UrApp treatment arm participants will follow the same procedures as described above for the SOC arm. For participants who do not own an iPhone, an iPhone will be loaned for the duration of the study. Caregivers/parents will download UrApp at the baseline visit. UrApp contains instructional videos to guide users. Participants will be instructed to test use the app, and all questions/difficulties using the app will be recorded by site research staff and resolved. The telephone number of the patient's provider will be entered into UrApp. Participants will be able to call their providers directly through UrApp. The email addresses of the local study staff and Emory's study staff will also be entered. UrApp

will automatically e-mail test results to the research staff when elected by the users. During the planned contacts in months 1-3 and 5-7, as described for the SOC arm, research staff will also inquire about any questions/technical issues with UrApp. These issues will be recorded and resolved. Participants will be asked by study staff, and reminded by the app, to call their providers and send urine testing results to the study staff whenever there is a relapse or remission. When the study staff receives alerts of a relapse/remission via UrApp, the information will be communicated to the treating physician within 1 business day. By the study staff receiving and monitoring urine testing results, we will be able to track participant behavior in notifying their physicians.

Measures/Materials

1) Baseline measures will be collected at the baseline visit between 2-6 weeks after NS diagnosis.

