Demographic characteristics of the patient caregiver (UrApp user) and the patient will be collected from the medical chart and by participant questionnaire. Variables will include: caregiver age, gender, race/ethnicity, income level, and educational level; patient age, gender, and race/ethnicity. As one inclusion criteria for trial participation is ownership of an iPhone, examination of demographic variables will provide information on the representativeness of the cohort to the general NS population and the generalizability of study findings. Baseline self-efficacy and QoL will be assessed by surveys. Caregiver self-efficacy will be assessed by a survey adapted from the Self-Efficacy for Managing Chronic Disease 6-Item Scale (Stanford Patient Education Research Center). The survey will include 3 questions with a scale of 1/not at all confident to 10/totally confident. Patient/caregiver-reported QoL will be assessed by using the 23-item Patient-Reported Outcomes Measurement Information System - Pediatric Quality of Life Inventory (PedsQL). PedsQL was developed as part of the NIH Roadmap Initiative to create universal measures for patient-reported outcomes, and contains questions in the domains of social-peer, depression, anxiety, mobility, and function. The survey has been found to have validity and feasibility in children and adolescents with NS.²² Caregivers and patients ages 5-17 will be surveyed with parent or patient forms, respectively.

2) Outcome measures will be collected at 6 and 12 months via caregiver surveys, medical chart review, and urine protein logs (UrApp data logs for the UrApp arm). We will perform 4 follow-up attempts within a 1-month timeframe to increase survey responses. Adherence to medications will be evaluated via caregiver survey with the validated 4 question Morisky, Green, and Levine (MGL) Adherence Scale.²³ We define adherence as a score of ≥ 3 on the MGL scale. Adherence with urine monitoring will be evaluated with a newly created questionnaire (Figure 4). In addition, UrApp data log (UrApp arm)

- 1) On average in the past month, how often did you check your child's urine for protein? (Once a week, 2-4 times a week, or 5-7 times a week)
- 2) In the past month, have you reduced how often you check your child's urine because he/she is in remission? (Yes or No)
- 3) In the past month, have you increased how often you check your child's urine because he/she is in relapse? (Yes or No)

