Figure 4. Urine protein monitoring questionnaire.

and urine protein logs (SOC arm) will also be collected to obtain the frequency of monitoring. *A priori*, we define adherence with urine protein monitoring as checking, on average, at least 2 times a week in the month preceding the assessment. Self-efficacy and QoL surveys will be administered in the same way as during the baseline visit. Relapse detection: patient medical charts will be reviewed for occurrence and frequency of delayed relapse reporting; defined as a relapse not reported to the treating physician until clinical manifestations or complications have occurred and/or only discovered during planned or unplanned visits or hospitalizations. Hospitalizations: medical records will be reviewed for the primary reason for admission and NS disease complications: bacterial peritonitis, septicemia, shock, blood clot(s), acute kidney injury, and seizures from hyponatremia or hypertension.

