Analysis will follow the intention-to-treat principle to preserve the integrity of the randomization. Primary outcomes, adherence with urine monitoring and medications, will be analyzed via Chi-square test to compare the proportions of adherent patients in the UrApp vs SOC arms at 6 and 12 months. Results will be presented as group proportions and difference in proportions with associated 95% CIs. In an adjusted analysis using a generalized linear mixed model, we will examine the changes over time by testing the treatment arm (UrApp vs. SOC) by time (6 and 12 months) interaction. Models will include site as a random effect and adjust for any baseline characteristic differences between groups (including sex as a variable). Self-efficacy and QoL measures will be analyzed using linear mixed models. Models will include the effect of treatment (UrApp vs. SOC), time (baseline, 6 and 12 months), and the treatment by time interaction. Study center will be included as a covariate and/or a random effect. Post-hoc pairwise comparisons will be used to compare specific points in follow-up (6 and 12 months) to baseline within and across groups. Results will be presented as differences in means with associated 95% CIs. Baseline characteristics will be included in the models as covariates in an adjusted analysis. Three-way interactions will be utilized to explore the role of demographic characteristics and their association with treatment response. While not adequately powered to conduct a moderator analysis, effect sizes will be calculated by subgroup and will inform a future, full-scale study. Delayed relapse diagnosis and hospitalizations will be compared between the treatment arms using Poisson regression under the framework of generalized linear mixed models or generalized estimating equations to account for correlated data collected from the same individuals. Baseline characteristics will be included in the models as co-variates. Analysis will be guided by [name], and carried out using SAS v.9.4 (Cary, N.C.).

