Medication adherence survey		✓		✓	✓
Urine testing adherence survey		✓		✓	✓
Schedule follow-up	✓	✓	✓	✓	
Stipend distribution³		✓		✓	✓
Clinical information CRF⁴		✓			
Hospitalizations and Relapses CRF⁴				✓	✓

Abbreviations: CRF, clinical reporting form; NS, nephrotic syndrome, V, visit

¹Enrollment visit can be performed on the same day as the Baseline Visit

²May be performed over the telephone or in-person

³\$20

⁴Completed by the research staff

UrApp Arm

	Enrollment ¹	Baseline (Time 0)	V1 ²	V2	V3
Acceptable time-frame	2-6 weeks after NS diagnosis	2-6 weeks after NS diagnosis	1-3 months	5-7 months	11-13 months
Consent/Accent	✓				
Randomization		✓			
Education material (folder and video)		✓			
Urine test strip (2 bottles) distribution (check expiration date)		✓		✓	
Instruct: check urine daily and call provider for relapse/remission		✓	✓	✓	
Download UrApp and enter ID, clinic contact number, and Emory e-mail address		✓			
Demographic survey		✓			
Self-efficacy survey		✓		✓	✓
QoL surveys (parent and child)		✓		✓	✓
Health app perception survey		✓			
UrApp feedback survey				✓	✓
Screening for issues or adverse events			✓	✓	✓
Medication adherence survey		✓		✓	✓
Urine testing adherence survey		✓		✓	✓
Interview⁵				✓	✓
Schedule follow-up	✓	✓	✓	✓	
Stipend distribution³		✓		✓	✓
Clinical information CRF⁴		✓			
Hospitalizations and Relapses CRF⁴				✓	✓
Approach for stakeholder committee (Emory site only)					✓

Abbreviations: CRF, clinical reporting form; NS, nephrotic syndrome, V, visit

¹Enrollment visit can be performed on the same day as the Baseline Visit

²May be performed over the telephone or in-person

³\$20; \$50 will be sent from Emory directly to the participants at 6 and 12m for completed interviews

⁴Completed by the research staff

⁵Will be performed via Zoom, conducted by the Emory staff. Can be performed in-person or via the phone for participants at the Emory site.

SECTION 4: DETAILED TRIAL PROCEDURES

PARTICIPANTS

1. Recruitment Target

60 participants will be recruited from the nephrology clinics of CHOA (Emory), OHSU, UMN, and MUSC between Sept. 2019 – March 2022. We will plan a recruit to replace up to 20%.

2. Screening

1. A systemic screening procedure at each site is crucial to meeting the recruitment target.
2. Recommended screening methods include:
 - a. Screen the inpatient census every day Monday – Friday for patients newly diagnosed with nephrotic syndrome

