 - b. Screen outpatient clinic appointments once a week for patients with newly diagnosed nephrotic syndrome
 - c. Discuss the study with division providers and once a month send out reminders for patient referrals to the study
3. As much as possible, approach potential participants in person during an admission or clinic visit to discuss the study and perform screening of the inclusion and exclusion criteria (Appendix A. Participant Screening Checklist).
4. A Screening and Enrollment Log needs to be completed on an ongoing basis and submitted to the Emory site every 6 months (Appendix B. Screening Log).

3. Inclusion Criteria

1. Caregivers of patients ages 1-17 years
2. Steroid sensitive NS diagnosed within 42 days at enrollment
 - a. Clinical diagnosis with edema, nephrotic range proteinuria (urine protein to creatinine ratio >2 mg/mg, or ≥ 300 mg/dL or $\geq 3+$ protein on urine dipstick), and hypoalbuminemia ≤ 2.5 g/dL
 - b. Resolution of proteinuria (negative/trace protein on urine dipstick) within 4 weeks of corticosteroid treatment
3. Access to internet/WIFI access in the home
4. Caregiver proficiency with the English language

4. Exclusion Criteria

1. End-stage kidney disease
2. Renal transplantation
3. Clinical or histologic evidence of secondary NS (e.g. systemic lupus erythematosus)

5. Consent / Assent and Enrollment

1. Written caregiver consent, patient assent (if applicable) will be obtained at enrollment.
 - a. Appendix C1: Consent
 - b. Appendix C2: Assent

2. Enrollment visit may be combined with the Baseline Visit, both of which must take place between 2-6 weeks of diagnosis.

Telephone/Virtual option:

1. Study can be introduced for either arm over the telephone or over a tablet with video conferencing.
2. The phone call can be conducted by research coordinators over the secure telemedicine solution, Zoom (<https://Zoom/>), so that research division's research phone number can be displayed instead of personal numbers of coordinators. An IRB approved telephone consent form should be used
3. Over the tablet, site teams will use Zoom video conferencing with candidate participants who are seen in clinic. The tablet will be set up by clinicians who are seeing the potential participants for a clinical indication. The telephone consent form will also be used.

BASELINE VISIT

Once consent / assent has been obtained, open one envelope to assign participants to either the UrApp or SOC arm.

SOC Arm

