1. Provide the participants with a folder of educational material on nephrotic syndrome (Appendix D1-D9. Educational Material).
 2. Play the video on "Why Check Urine Protein".
 3. Confirm that the participants understand how to check urine for protein and the definitions for a new disease relapse and remission. Review Appendix D2 as needed to confirm understanding.
 4. Instruct families to check urine daily and log results onto the Urine Protein Log (Appendix D9).
 5. Instruct families to call their provider within 1 business day for relapses and remissions.
 6. Hand out 2 bottles of urine test strips, check expiration date
 7. Administer surveys (Appendix E)
 - a. Demographics (Appendix E1)
 - b. Self-Efficacy (Appendix E2)
 - c. PedsQL Parent Report (Appendix E3)
 - i. pick the appropriate patient age group: 2-4, 5-7, 8-12, 13-18
 - d. PedsQL Child Self Report (Appendix E4)
 - i. pick the appropriate patient age group: 5-7, 8-12, 13-18
 - e. Medication-take Scale (Appendix E6)
 - f. Urine-monitoring Scale (Appendix E7)
 8. Schedule V1 (can be a phone call) and V2
 9. Distribute stipend for \$20
- After the study visit:
10. Complete Clinical Information CRF (Appendix F)
 11. Complete Baseline Visit Data Entry on the Redcap Link.

UrApp Arm

1. Provide the participants with a folder of educational material on nephrotic syndrome (Appendix D1-D9. Educational Material).
 2. Play the video on “Why Check Urine Protein”.
 3. Confirm that the participants understands how to check urine for protein and the definitions for a new disease relapse and remission. Review Appendix D2 as needed to confirm understanding.
 4. Instruct families to call their provider within 1 business day for relapses and remissions.
 5. Hand out 2 bottles of urine test strips, check expiration date
 6. For participants without iPhones, loan participants a study iPhone. Sign Appendix K. iPhone Return Agreement.
 7. Download UrApp onto the participant iPhone, instruct participant to go through UrApp functions and watch video on “Checking Urine with UrApp” (automatically starts).
 8. Enter Participant ID, physician contact number (local site clinic number), and Emory research team e-mail address ([contact]) under UrApp “Settings”.
 9. Administer surveys (Appendix E)
 - a. Demographics (Appendix E1)
 - b. Self-Efficacy (Appendix E2)
 - c. PedsQL Parent Report (Appendix E3)
 - i. pick the appropriate patient age group: 2-4, 5-7, 8-12, 13-18
 - d. PedsQL Child Self Report (Appendix E4)

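### Baseline adherence is collected for both primary outcomes but has no prespecified role in the analysis, and the urine item's one-month recall can reach back before diagnosis

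*Combined protocol and SAP*

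**What the plan says.** **Collection.** The SOC Arm and UrApp Arm tables in Section 3 tick the "Urine testing adherence survey" and the medication adherence survey at Baseline, V2 and V3. The Baseline Visit lists in Section 4 include both surveys for both arms. The baseline paragraph under Measures/Materials (Section 2, Aim 1) names only demographics, self-efficacy and QoL. It places adherence among the outcomes collected at 6 and 12 months.

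**Timing.** The same paragraph states: "Baseline measures will be collected at the baseline visit between 2-6 weeks after NS diagnosis". The inclusion criteria in Section 4 require "Steroid sensitive NS diagnosed within 42 days at enrollment".

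**Wording.** Item 1 of Figure 4 opens "On average in the past month, how often did you check" and offers three answers: once a week, 2-4 times a week and 5-7 times a week. Adherence is defined as "checking, on average, at least 2 times a week in the month preceding the assessment".

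**Analysis.** The primary outcomes are compared by Chi-square at 6 and 12 months. The adjusted generalized linear mixed model works by "testing the treatment arm (UrApp vs. SOC) by time (6 and 12 months) interaction", with site as a random effect and adjustment for baseline characteristics on which the groups differ. In the self-efficacy and QoL models, baseline is one of the time levels.

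**Order of events.** In Section 4 the envelope is opened after consent. Education follows, then the app download in the UrApp arm, and the surveys come after these. By the virtual route the surveys are e-mailed after the video visit, with up to four weekly telephone reminders.

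**The concern.** The baseline value of an outcome is usually the first candidate for covariate adjustment. Here it is collected for both primary outcomes, yet the plan does not say what it is for. The only way in is a clause triggered by observed differences between the arms. Whether baseline adherence is in the adjusted model would then be decided after the data are seen, and by a criterion (imbalance) that is not the same as prognostic value.

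The second issue is what the urine answer measures. If the recall period is longer than the time since diagnosis, the same testing habit can be recorded as a lower rate in a family seen early than in one seen late. Tabulated or used as worded, the baseline answer could partly reflect days since diagnosis.

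At stake are the interpretability of the baseline table and the credibility and precision of the adjusted analysis. The unadjusted primary comparison is not at stake.

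**Working it through.** **1. The plan's own figure.** Inputs from Participants and settings (Section 2, Aim 1): 60 participants randomized 1:1, 20% drop-out, 55% versus 90%, two-sided pooled Z-test at 0.05. Evaluable per arm: 30 × 0.8 = 24. Exact binomial enumeration of that test gives 82.0%, which matches the stated 82% (the normal approximation gives 79.4%). No baseline answer enters this calculation.

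**2. Overlap of recall period and diagnosis.** Inputs: visit on day d = 14 to 42 and a month taken as 30 days. Days of the recall period before diagnosis = max(0, 30 − d). This gives 16 on day 14, 9 on day 21, 1 on day 29, and none from day 30.

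**3. Effect if the caregiver averages over the full month.** Assume no testing before diagnosis. Reported rate = true rate since diagnosis × min(1, d/30). The true rate needed to reach 2 a week is 2 ÷ (d/30):

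| Visit day | d/30 | True rate needed | Daily tester reports |
|---|---|---|---|
| 14 | 0.47 | 4.3/week | 3.3/week |
| 21 | 0.70 | 2.9/week | 4.9/week |
| 28 | 0.93 | 2.1/week | 6.5/week |
| 30 or later | 1 | 2.0/week | 7/week |

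So the binary status can flip only for true rates from 2 to below 4.3 on day 14, and from 2 to below 2.9 on day 21. With a 28-day month the upper limits are 4.0 and 2.7. A daily tester is still adherent on day 14, but moves from the 5-7 answer to the 2-4 answer.

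**4. Effect if the caregiver averages only since diagnosis.** Reported rate = true rate, so the error is zero on every visit day.

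**5. Follow-up assessments.** At V2 (5-7 months) and V3 (11-13 months) the past month lies wholly after diagnosis. The mismatch is confined to baseline.

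**6. Late answers by the virtual route.** An answer given after four weekly reminders comes about 28 days after allocation. Then about 28/30 = 93% of its recall period is post-randomisation.

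**7. Room for a covariate.** Expected non-adherent outcomes at one time point under the planned rates: 24 × 0.45 + 24 × 0.10 = 10.8 + 2.4 = 13.2.

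**8. Possible gain in precision.** The documents give no correlation between baseline and later adherence. As an assumption, on the risk-difference scale the variance ratio is roughly 1 − r²: 0.96 at r = 0.2 and 0.91 at r = 0.3. At r = 0 a simulation with 24 per arm gave about 1.02, a loss of about 2%. These values do not carry over directly to the planned mixed model.

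**The case against.** Several points on the other side are sound.

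- **Misclassification is not shown.** The item asks for a weekly rate, and a caregiver may well answer for the days since diagnosis. A reader might infer that every family seen before day 30 is misclassified. The documents do not support this: an early visit creates only exposure to the problem, and a flip needs both full-month averaging and a true rate in the narrow bands above. The documents also do not give the distribution of visit days. Eligibility requires documented resolution of proteinuria, which may limit very early visits.
- **The answer is not necessarily wasted.** The imbalance clause could admit baseline adherence. What stands is that the plan does not say so, and that entry would depend on the data.
- **No primary result changes.** A reader might infer bias in the arm comparison or a loss of the stated power. Neither follows: the Chi-square tests and the power do not use the baseline answer, and time since diagnosis does not depend on arm.
- **A large gain in precision cannot be promised.** With baseline adherence p and a 90% outcome rate, the largest possible correlation is (p − 0.9p) ÷ √[p(1 − p) × 0.09]. For assumed p of 50%, 60% and 70% this is 0.33, 0.41 and 0.51.
- **The covariate is not strictly pre-randomisation.** The surveys follow allocation, education and app download, and may be answered weeks later. This stands fully, so any adjustment must deal with it.
- **Little recruitment remains.** The document is dated 17 February 2022 and recruitment is planned to March 2022. Rewording would reach few families and would create two versions of the item.
- **Appendix E7 is not reproduced.** That it is the Figure 4 questionnaire is inferred. The wording of the medication survey is not shown either, so the recall point concerns the urine item only.

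**Conclusion.** The concern holds in a limited form. Baseline adherence is collected for both primary outcomes and has no prespecified role, while the secondary self-efficacy and QoL models use their baseline values. That rests on the text alone.

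The recall mismatch is possible rather than demonstrated. It concerns only visits on days 14 to 29, and its effect ranges from none to a downward shift large enough to flip the coded status within the bands above. This assumes that the baseline form is Figure 4 and that no testing took place before diagnosis.

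The consequence falls on the adjusted analysis and the description of the cohort at baseline. This is a worthwhile, inexpensive improvement to a pilot's plan, not a threat to its primary comparison. The main argument for it is to remove a data-driven choice. The precision gain is unknown and may be slight.

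**What to change.** 1. **Analysis paragraph and baseline measures, Section 2, Aim 1.** Prespecify baseline urine-testing frequency and baseline MGL score as fixed covariates, each in the adjusted 6- and 12-month model for its own outcome, whatever imbalance is observed. Keep the unadjusted Chi-square tests as planned. Add both to the list of baseline measures.
2. **Baseline Visit, Section 4.** Have the adherence surveys completed before the envelope is opened. For families already enrolled, treat an answer as baseline only if its completion date shows that it was given at the baseline visit. Add a sensitivity analysis without the covariate.
3. **Figure 4, item 1.** For any remaining baseline visits, ask about the period since diagnosis. For all families, report the baseline answer with days from diagnosis to survey completion, so that early and late answers can be told apart.

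Cost: a few sentences in the analysis section, a change in the order of the baseline visit, one wording change, and an interval computed from dates that should already be on file. The downsides are a small loss of precision if baseline and later adherence are unrelated, and one more covariate in a model with about 13 expected non-adherent outcomes per time point. Some enrolled families may also have no usable baseline answer, so the plan should say how they are handled in the adjusted model.

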Summary of work to date: We have 1) demonstrated the significance of self-management and the unmet need for a support tool in childhood NS; 2) established feasibility and interest in using mHealth interventions among NS patient caregivers; 3) soundly designed UrApp features that are grounded in theory with excellent preliminary user feedback and usability; and 4) established technical innovation and validity. *Our central hypothesis is that the use of a UrApp-based self-management support system will improve adherence with urine monitoring and medications.* We also predict that caregiver self-efficacy, patient and caregiver quality of life (QoL), and relapse detection will improve while hospitalization rates will decline.

In this proposal, we aim to rigorously test our hypotheses to gain sufficient preliminary data to advance the scalability and capacity of the intervention to impact outcomes in the real world. We plan to address crucial domains within the RE-AIM framework: efficacy (pilot trial to evaluate UrApp's impact on outcomes and stakeholder engagement to determine outcomes important to users), adoption (process evaluation to determine barriers/facilitators of app use and stakeholder involvement to refine the intervention design and create strategies to increase recruitment for a future trial), implementation (process evaluation of UrApp implementation and stakeholder involvement to redesign the intervention to ensure appropriate implementation), and maintenance (process evaluation to determine influences on use retention and user/stakeholder involvement to refine intervention design and plan a feasible clinical trial).²⁰ The “reach” domain is outside the scope of the pilot trial, though we have planned technical updates of UrApp to increase the number of iPhone versions it supports. Our specific aims are:

Aim 1. Evaluate the preliminary efficacy of UrApp among caregivers of children with nephrotic syndrome in a pilot trial. Participants will be randomized 1:1 to UrApp or SOC and followed for 1 year. Primary outcomes are medication and urine monitoring adherence. Secondary outcomes are self-efficacy, patient-reported quality of life, relapse detection, and hospitalizations.

Aim 2. In parallel with the pilot trial, perform a mixed-methods process evaluation of the

implementation of UrApp to determine the influences on its effectiveness.

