Site PIs at CHOA, OHSU, and UMn met and agreed on all procedural details, including standards for usual care, led by [name]. A Manual of Procedures was created. Each site will obtain local IRB approval (central IRB not required for a K23). Data entry and collection will be centralized via a REDCap database built by [name].

The ECPI coordinator and [name] will provide data collection and entry training to the site PIs and coordinators.

Aim 1. Evaluate the preliminary efficacy of UrApp among caregivers of children with nephrotic syndrome in a pilot trial.

Participants and settings: 60 participants will be recruited from the nephrology clinics of CHOA,

OHSU, UMn, and MUSC. Sample size of 60 participants (randomized 1:1) will achieve 82% power to detect a 35% point difference in adherence with urine monitoring (primary outcome), with 20% drop-out. Sample size and power estimates are based on an adherence rate of 55% in the control group and 90% in the UrApp intervention group. These estimates are based on our single center experience with SOC⁸ and our experience with text messaging for NS monitoring, where 94% of the participants continued to check urine and provide results via text messaging at the end of 1 year (manuscript under review). Power was calculated using a two-sided Z-test with pooled variance at 0.05 type I error rate using PASS v. 14.0.8 (Kaysville, UT). Our sample size exceeds the recommended minimum of 12 participants per arm for pilot studies.²⁰

Inclusion criteria: Caregivers of patients ages 1-17 with steroid sensitive NS diagnosed within 42 days at time of enrollment; access to WIFI/internet; and proficiency with the English language.

Exclusion criteria: end-stage kidney disease; renal transplantation; and clinical or histologic evidence of secondary NS (e.g., systemic lupus erythematosus).

Procedures: Participants will be enrolled and randomized 1:1 to UrApp or SOC treatment arms at the baseline visit between 2-6 weeks after diagnosis. Recruitment will continue for 2 years, and participant follow-up will be 1 year. Written caregiver consent and patient assent (verbal for children ages 6-10 and written for children ages 11 and above) will be obtained per local IRB guidance.

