Procedures: Stakeholder members will include: 1) Drs. [name] and [name]; 2) GT research engineers with human-computer interaction expertise who developed UrApp and are intimately aware of technical possibilities/restrictions; 3) 5 patient caregivers in the UrApp arm who have completed 12 months follow-up. Participants in the UrApp arm at Emory will be approached for interest in joining the stakeholder committee during the pilot trial. Four face-to-face stakeholder meetings with a virtual (Zoom) conference option for members who cannot be present will be conducted. Meetings will be held every 1-3 months, with the first meeting starting at the end of pilot trial recruitment, when we anticipate having 6-months follow-up data on at least half of the trial participants. Caregiver members will be compensated \$75 for each meeting, and food/drinks will be provided (fair compensation under *partnership*). Meeting 1 will focus on introducing members to each other and building relationships (*reciprocal relationships* and *trust*). We will outline the goals of the stakeholder committee to refine UrApp and plan a future trial (*co-learning*). A summary of the trial results to date on UrApp efficacy and process evaluation will be shared (*transparency, honesty*), and members will be invited to share their perspectives and interpretation of the trial results (*co-learning*). Meetings 2-4 will

include a review of updated trial results. Informed by the trial results, the committee will iteratively plan UrApp refinement (*transparency, co-learning, and reciprocal relationships*). Caregivers will provide input on outcomes most important to users. The investigators will use the feedback to iteratively develop measures/procedures to be reviewed at subsequent meetings (*co-learning, reciprocal relationships*). Caregivers will provide feedback on the protocols to improve recruitment and retention.

SECTION 3: TRIAL TIMELINE AND RESEARCH TASKS

SOC Arm

	Enrollment ¹	Baseline (Time 0)	V1 ²	V2	V3
Acceptable time-frame	2-6 weeks after NS diagnosis	2-6 weeks after NS diagnosis	1-3 months	5-7 months	11-13 months
Consent/Accent	✓				
Randomization		✓			
Education material (folder and video)		✓			
Urine test strip (2 bottles) distribution (check expiration date)		✓		✓	
Instruct: check urine daily and call provider for relapse/remission		✓	✓	✓	
Demographic survey		✓			
Self-efficacy survey		✓		✓	✓
QoL surveys (parent and child)		✓		✓	✓
Screening for issues or adverse events			✓	✓	✓

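### Two primary outcomes tested at two visits make four primary comparisons with no primary visit, order, success rule or adjustment; the stated 0.05 and 82% power describe only one of them

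*Combined protocol and SAP*

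**What the plan says.** All references are to the combined protocol and SAP.

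- **Section 2, Goals/Aims, Aim 1** gives two outcomes equal standing: "Primary outcomes are medication and urine monitoring adherence".
- **Section 2, Study Design, Aim 1, Analysis** applies one test to both: "Primary outcomes, adherence with urine monitoring and medications, will be analyzed via Chi-square test", used "to compare the proportions of adherent patients in the UrApp vs SOC arms at 6 and 12 months". Differences in proportions get unadjusted 95% confidence intervals. The adjusted analysis mentioned there is covariate adjustment in a mixed model, not adjustment for multiplicity, and it adds a treatment-by-time test.
- **Section 2, Study Design, Aim 1, Participants and settings** powers the trial at 82% "to detect a 35% point difference in adherence with urine monitoring (primary outcome), with 20% drop-out", and adds: "Power was calculated using a two-sided Z-test with pooled variance at 0.05 type I error rate". No visit is named. Medication adherence has no assumed rates and no power. The 90% assumed for the UrApp arm draws on a text-messaging study in which "94% of the participants continued to check urine and provide results via text messaging at the end of 1 year".
- **Section 2, Study Design, Aim 3, Procedures** has the "first meeting starting at the end of pilot trial recruitment, when we anticipate having 6-months follow-up data" on at least half of participants. At that meeting, "A summary of the trial results to date on UrApp efficacy and process evaluation will be shared". Meetings 2 to 4 review updated results.

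**The concern.** Two outcomes at two visits give four comparisons that all carry the label primary. The plan does not say which one answers Aim 1, or whether one, some or all must favour UrApp. If the four results disagree, the conclusion depends on a choice made after the fact. If any one significant result is read as success, the 5% error rate in the power statement does not hold for the trial's conclusion.

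Timing adds to this. Efficacy results are to be shared from the end of recruitment, when 6-month data will be more complete than 12-month data. As written, the deciding outcome and visit could still be open when results are first seen. The pilot is meant to inform a full-scale trial, so an overstated or selectively read result would carry forward.

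**Working it through.** **Inputs from the plan.** 60 participants randomized 1:1, 20% drop-out, 55% versus 90% adherence, two-sided 0.05, pooled-variance Z-test (equivalent to the Chi-square test without continuity correction). Evaluable per arm: 60 × 0.8 / 2 = 24.

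**1. The plan's own figure.** Summing the binomial probabilities of every outcome pair that the pooled Z-test rejects, at 24 per arm, gives power of 82.0%. The stated 82% is reproduced. (The normal approximation gives 79.4%.) It is the power of one comparison at 0.05.

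**2. Size of a single test.** By the same enumeration with equal rates in both arms, the true error is 5.8%, 5.2% and 4.7% at a common rate of 55%, 72.5% and 90%. One named comparison therefore holds close to 5%.

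**3. Any one of four counts.** Under independence, 1 − 0.95⁴ = 0.185, and the Bonferroni bound is 4 × 0.05 = 0.20. The four tests share participants, so the planned test was simulated at 24 per arm (40,000 replicates, correlated binary data from a latent normal). Chance of at least one false positive:

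| Correlation between visits / outcomes | Null 55/57% | Null 72.5/74.5% | Null 90/92% |
|---|---|---|---|
| 0 / 0 | 21.2% | 19.2% | 16.3% |
| 0.5 / 0.2 | 20.1% | 18.7% | 15.8% |
| 0.8 / 0.5 | 18.4% | 16.9% | 14.3% |
| 0.95 / 0.5 | 16.3% | 15.4% | 13.1% |

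Null rates are urine / medication. The 55% is the plan's control rate. The 57% is 100% less the 43% medication nonadherence in Background and Significance. The other rates and all correlations are assumptions. Values above 18.5% arise because a single test runs slightly above 5% at these sample sizes.

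**4. All must succeed.** Assume medication adherence rises from 57% to 90% (the 90% is an assumption). Exact power for that test alone is 78.0%.

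- Both outcomes at one visit: 0.820 × 0.780 = 0.64 if independent, about 66% at the highest correlations above.
- All four comparisons: 0.64² = 0.41 if independent, about 56% at the highest correlations.

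With smaller medication effects these figures are lower.

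**5. Power under possible repairs**, urine monitoring, exact, 24 per arm:

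| Rule | Level per test | Power |
|---|---|---|
| One named comparison, or first in a fixed sequence | 0.05 | 82.0% |
| Alpha split over two | 0.025 | 73.1% |
| Alpha split over four | 0.0125 | 62.5% |

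In a fixed sequence, a second urine-monitoring test with the same effect is reached and passed with probability 0.820² = 0.672 if independent. This approaches 82% as the correlation between visits rises.

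**The case against.** The strongest reply has four parts.

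- **The inflation assumes a rule the plan does not contain.** The central hypothesis predicts improvement in urine monitoring and in medications. Read as requiring both, it does not inflate error. That is correct, and the 13% to 21% is conditional. But the conjunctive reading has its own cost (step 4): the 82% is then no longer the chance of success. Neither reading matches the power statement.
- **This is a pilot of preliminary efficacy**, also justified by a pilot-study minimum of 12 per arm, with no go/no-go rule tied to a p-value and intervals promised for every comparison. This limits the seriousness. It does not remove the point, because the plan chose hypothesis tests, an error rate and a power claim, and intervals do not identify the deciding result.
- **The plan already leans towards urine monitoring at 12 months.** It does lean that way on the outcome, but Goals/Aims and the Analysis text list both outcomes equally. The case for 12 months is partial: the 55% control rate comes from a retrospective study of the first 3 years after diagnosis.
- **Demoting a named primary outcome late carries risk.** Recruitment began in September 2019, so some 12-month data may already exist, and Section 6 has the lead investigator reviewing entries monthly. It may be hard to show that the choice preceded any knowledge of results. This stands, and is why the change must be dated and disclosed. Declaring all four comparisons to be estimates with no confirmatory claim would be less intrusive and defensible, but the 0.05 and 82% statement would then need rewording.

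**Conclusion.** The concern holds. Four comparisons are labelled primary, and the stated error rate and power belong to one of them, at an unnamed visit. If any one result suffices, the false-positive chance is about 13% to 21% instead of 5%, given the assumed correlations and null rates. If both outcomes must succeed at one visit, power is about 64% to 66%; if all four must, about 41% to 56%, even with an optimistic assumed medication effect. The 82% itself is correct; its scope is the problem. Because this is a pilot, the change is one that should be made, not one without which the trial cannot proceed.

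**What to change.** Reconcile Goals/Aims, the sample-size text and the Analysis text by naming one primary comparison: urine-monitoring adherence at 12 months, UrApp versus SOC, two-sided 5%. The 12-month choice is an inference, but it fits the 1-year follow-up and the end-of-year figure behind the 90% assumption. Make 6-month urine monitoring and medication adherence at both visits secondary, reported with 95% confidence intervals, or test them after the primary comparison in a stated fixed order. Record the decision and its date before any results by arm are reviewed, including at the first stakeholder meeting. State plainly what data had already been seen.

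The cost is wording and a dated record: no added participants or data, and the 82% is kept. The 6-month and medication results could no longer support a stand-alone primary claim. The document is dated February 2022 and recruitment runs to March 2022, so the report must disclose this as a late change to a named primary outcome.
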